1 PROTOCOL SUMMARY

1.1 SYNOPSIS

| | | |
|---------------------------|--|---|
| Title: | Standardized Patient-Centered Medication Review in Home Hospice | |
| Grant Number: | R21 AG060017 | |
| Study Description: | Background Over 1.3 million Americans aged 65 years and older receive hospice services annually and 45% are cared for at home. ⁵ These patients are prescribed an average of 10-12 medications daily ^{6 7} and have progressively declining organ function that increases their risk of drug-related harm ^{9 10} . Furthermore, many take questionably beneficial medications ^{11 12 13} until death while simultaneously being prescribed an increasing number of end-of-life (EOL) symptom management drugs. This changing combination of medications contributes to stress and confusion for family caregivers (FCG) who are responsible for their management and administration. ^{14 3} | |
| Objectives*: | Study Design This protocol describes a pilot multi-site cluster randomized trial of a behavioral education intervention to standardize hospice clinician approach to medication management support for family caregivers of patients in home hospice vs attention control of an educational handout about medication management for older adults education from the NIA. The primary outcome is feasibility and acceptability of the trial as measured by trial enrollment and completion. Secondary outcomes include family caregiver medication administration burden, family caregiver satisfaction with care, polypharmacy, medication regimen complexity, patient quality of life, patient symptom burden, adverse events including hospitalizations and emergency department and adverse drug withdrawal events. | |
| Objectives*: | Primary Objective: | To determine, among patients admitted to home hospice with life-limiting illness, the acceptability and feasibility of enrollment and completion of a trial of a medication support program delivered by home hospice clinical staff. |

| | |
|----------------------|---|
| Secondary Objective: | Secondary analysis will investigate the following outcomes: |
| | 
• Family caregiver medication burden, as measured by the Family Caregiver Medication Administration Hassle Scale.• Family caregiver satisfaction with care, as determined by likelihood to recommend• Polypharmacy• Potentially inappropriate medication use, as determined by a modified Medication Appropriateness Index• Medication regimen complexity, as measured by the Medication Regimen Complexity Scale• Medication changes• Adverse drug withdrawal events, as measured by a single item single item measure of change in medication since last visit and associated symptom change• Patient Quality of life (QOL), as measured by the McGill QOL Questionnaire (MQOLQ)• Patient Symptoms, as measured by the Edmonton Symptom Assessment System (ESAS)• Performance status, as measured by the Karnofsky Performance Status sale (KPS)• Unanticipated Events (whether study-related or not), as measured by time to first important event, consisting of:
○ admission to a hospital for any reason○ admission to an emergency department for any reason |

- Overall survival, as measured by time-to-death

Endpoints*:

Primary Endpoint: Trial completion

Secondary Endpoints: As described in Secondary Objectives

Study Population:

Eligible participants are adults aged 65 years and older with advanced life-limiting illness with an estimated prognosis of 1-6 months who are prescribed 5 or more medications and their family caregivers.

Phase* or Stage:

Feasibility Trial

**Description of Sites/Facilities
Enrolling Participants:**

Hospice Sites. EOL practices vary regionally.¹³⁻¹⁵ Thus, we are partnering with two large, geographically distinct home hospice agencies to begin exploring the generalizability of SPECTORx nationally. Each agency has multiple offices serving different

local regions within their states. Care Dimensions (Massachusetts) has 2 offices serving 4 counties in Eastern MA, and CNS Home Health & Hospice (Utah) has 10 offices throughout Utah.

Description of Study Intervention/Experimental Manipulation:

The study intervention is a patient-centered medication review and FCG support program called “Standardized PatiEnt-CenTered medicatiOn Review (SPECTORx) in Home Hospice”. This intervention combines 3 innovative, complementary, educational programs that, together, train hospice staff to create a comprehensive, patient-centered, medication management plan. These evidence-based tools equip hospice staff: 1. to systematically identify medications that can be stopped or tapered using STOPPFrail (Screening Tool of Older Persons Prescriptions) criteria; 2. to discontinue medications appropriately; and 3. to educate and support FCGs with medication administration and management challenges. The SPECTORx program also creates an online learning community for hospice clinicians to promote ongoing education and practice change.

[figure not shown]
Study Duration*:

Estimated study duration from earliest enrollment to completion of data collection is 12 months.

Participant Duration:

Estimated time it will take for each individual participant to complete all study-related tasks (i.e. time from enrollment to patient death, discharge from hospice, or end of study) is 6 months.

1.2 SCHEMA

1.3 SCHEDULE OF ACTIVITIES

| STUDY PERIOD | | | | | |
|--|---|---------|---------|------------------------|----------------------|
| TIMEPOINT | Screening / Post-allocation Enrollment | | | Close-out | |
| | 2 weeks | 4 weeks | 6 weeks | 8 weeks and monthly | 24 weeks or death |
| ENROLLMENT | | | | | |
| Eligibility screening | x | | | | |
| Informed consent | x | | | | |
| FEASIBILITY | | | | | |
| SPECTORx Intervention | | | | | |
| Attention Control | | | | | |
| ASSESSMENTS (Source/Items) | | | | | |
| FCG/Demographics | x | | | | |
| FCG/Family Caregiver | x | x | x | x | x |
| Medication Administration | | | | | |
| Hassle Scale | | | | | |
| FCG/Potential medication related symptom change | | x | x | x | x |
| FCG/Patient Centered Medication Communication | x | x | x | x | x |
| FCG/Satisfaction with Care (Likelihood to recommend) | | | | | x |
| EMR/ PT Demographics | x | | | | |
| EMR/ PT Primary Hospice Admitting Diagnosis* | x | | | | |
| EMR/ PT Comorbid Illness* | x | | | | |
| EMR/PT Medications* | x | x | x | x | x |
| EMR/PT KPS* | x | x | x | x | x |
| EMR/PT Survival* | | x | x | x | x |
| EMR/PT Health resource utilization (hospital admissions, emergency department visits)* | | x | x | | x |

| | | | | | |
|---|---|---|---|---------------------------|---|
| EMR/Potential Drug Related Problem Screen | x | x | x | x | x |
| Patient/Potential Drug Related Problem | | x | | x (& monthly thereafter) | |
| Patient/MQOLQ | x | x | x | x | x |
| Patient/ESAS | x | x | x | x | x |

2 INTRODUCTION

2.1 STUDY RATIONALE

Need for a Comprehensive, Patient-Centered, Medication Review and FCG Support Program

A tremendous challenge in home hospice care is ensuring that medication prescribing is appropriately aligned to patients' goals of care and that medications are appropriately managed by FCGs.

There are no intervention studies addressing medication appropriateness in home hospice. Our literature review¹⁶ found one uncontrolled, retrospective study in geriatric palliative care that **reviewed and simplified** regimens by reducing unnecessary drug use by 65% (from 1.7 to 0.6 per patient).¹⁷ Investigators reported that 74% of patients used at least 1 unnecessary medication (defined as drugs with lack of indication, lack of effectiveness, or prolonged duration of therapy). Their study provided "proof of concept" that it is possible to systematically review and simplify medications in geriatric palliative care.¹⁷ However, such studies have focused on geriatrics^{18 19 20 21 22 23} and nursing homes,^{24 25} and not home hospice.

Few studies examine FCG medication management needs.^{14 3 26 27} FCGs have many challenges, including dealing with patients' non-adherence, deciding which medications to give, juggling administration times and monitoring for side effects.^{14 3} Furthermore, patient symptom outcomes depend on appropriate medication administration. (Figure 1) The implication is that high-quality, patient-centered care needs to address *both* medication appropriateness and FCG medication management support.

*Therefore, we propose a novel approach that trains hospice staff to (a) regularly **review, simplify, and align** patients' prescribed medications with their goals of care as their illness progresses,¹⁶ and (b) **support** FCGs' with education that empowers them to understand each medication's use, develop skills for safe administration, and understand when stopping medications may be beneficial.^{3 26}*

2.2 BACKGROUND

Polypharmacy for Home Hospice Patients is Burdensome, Harmful and Costly

Over 1.3 million Americans aged 65 years and older receive hospice services annually and 45% are cared for at home.⁵ These patients are prescribed an average of 10-12 medications daily^{6 7 8} and have progressively declining organ function that increases their risk of drug-related harm.⁹ Furthermore, many take questionably beneficial medications^{11 12 13} until death while simultaneously being prescribed an increasing number of end-of-life (EOL) symptom management drugs.⁸ This changing combination of medications contributes to stress and confusion for family caregivers (FCG) who are responsible who are responsible for patient medication management and administration.^{14 3}

Family (Informal) Caregivers Find Managing Complex Home Hospice Medication Regimens Stressful

Family (informal) caregivers are defined as “any relative, partner, friend or neighbor who has a significant personal relationship with, and provides a broad range of assistance for [an older person]”.⁴ Hospice is a particularly challenging setting for FCGs because they are responsible for complicated medication administration tasks that are *usually reserved for licensed healthcare professionals*.²⁸ An estimated 44 million adults, mostly women, provide this informal (i.e. unpaid) care.²⁹ They often feel inadequately prepared for this responsibility³⁰ and have fears about doing something wrong.^{28 30}

2.3 RISK/BENEFIT ASSESSMENT

2.3.1 KNOWN POTENTIAL RISKS

The risks and costs vs benefits of reducing polypharmacy for patients with advanced disease and their family caregivers remains a genuine clinical uncertainty. Multiple studies support the use of myriad individual chronic disease medications, such as statins, in elderly adults with appropriate indication. However, the benefit of continuing chronic disease medications after hospice admission on quality of life, family caregiver medication hassle, or patient survival is unknown. Simplifying medication regimens through a process of deprescribing is one remedy to medication complexity as death approaches, but may be associated with potential risk of stress to family caregivers about making decisions regarding stopping medications and additional potential risk of adverse drug withdrawal events after stopping medications - a particular concern when abruptly stopping medications with long half lives that are known to require tapering protocols.

2.3.2 KNOWN POTENTIAL BENEFITS

Multiple studies support reduction of polypharmacy in elderly patients with multi-morbidity. Less is known to support the benefit of medication discontinuation among patients in hospice. One exception is the question of benefit from stopping statins used for primary prevention among elderly patients with advanced illness, a question addressed in a randomized controlled trial of statin discontinuation by Kutner et al. These data show that statin discontinuation does not contribute to shortened survival, and may be associated with improved quality of life.

2.3.3 ASSESSMENT OF POTENTIAL RISKS AND BENEFITS

Polypharmacy has known patient burden and associated patient side effects. This is attributable to the accumulation of individual medication effects, and known drug-drug interactions resulting from complex medication regimens. For patients with life-limiting conditions who take one or more chronic disease medications along with symptom directed therapies, the balance of medication efficacy vs burden remains unclear. Finally, the psychological impact of using or discontinuing chronic disease medications in the setting of advanced life-limiting illness is largely unknown. Patients may feel relief when not

taking as many pills, anticipating the potential for fewer side effects, and paying less medication costs for medications not covered by hospice yet desired by the family. Conversely, there may be increase worry or distress when discontinuing a medication that a patient and their family was told would need to be taken for the rest of their lives.

3 OBJECTIVES AND ENDPOINTS

| OBJECTIVES | ENDPOINTS | JUSTIFICATION FOR ENDPOINTS | PUTATIVE MECHANISMS OF ACTION |
|-------------------------------|---|---|-------------------------------------|
| Primary | | | |
| Feasibility and Acceptability | 
 • Intervention Delivery to Hospice Staff • Patient and Family Caregiver Recruitment Goals • Completion of FCGs Assessments • Completion of Patient Assessments • Time for completing FCG assessments • Time for completing Patient Assessments • Yield of FCG Eligibility Criteria • Yield of Patient Eligibility Criteria | 
 • Measurements of Intervention Uptake • Measures of Recruitment Yield • Measure of Outcome Assessment Success | |
| Secondary | | | |
| Efficacy and Safety | 
 • FCG Burden • Medication Regimen Complexity • Patient-Centered Medication Communication | 
 • Primary Outcome for trial • Patient medication burden • Quality of prescribing for patients | |

| OBJECTIVES | ENDPOINTS | JUSTIFICATION FOR ENDPOINTS | PUTATIVE MECHANISMS OF ACTION |
|-----------------------------|--|--|-------------------------------------|
| | 
 Potentially Inappropriate Medications, as measured by modified Medication Appropriateness Index Medication changes Patient QOL, as measured by McGill QOL Questionnaire Patient Symptoms, as measured by Edmonton Symptom Assessment System (ESAS) Overall Survival Suspected Unexpected Serious Adverse Reactions (SUSAR) Drug Related Problems | 
 Key patient outcome Key patient outcome Key patient outcome Assessment of risk for study population Risk assessment for intervention | |
| Tertiary/Exploratory | | | |
| | | | |

4 STUDY DESIGN

4.1 OVERALL DESIGN

A pilot, single-blinded, cluster randomized, pragmatic trial of the SPECTORx intervention.

We will compare outcomes within and across 2 large, multi-office, hospice agencies from Utah and Massachusetts. Within each hospice agency, we will randomize 1 office to intervention and 1 office to attention control. Target enrollment is 30 FCG-patient dyads per agency (n=15 intervention, n=15 control), for a total trial target of n=60 FCG-dyads of patients aged ≥ 65 years, with an estimated life expectancy of >1 month, and polypharmacy (defined as ≥ 5 regularly scheduled daily medications).

4.2 SCIENTIFIC RATIONALE FOR STUDY DESIGN

This is a controlled study to evaluate the effect of a medication review, education and communication intervention on improving medication administration burden by family caregivers in home hospice. The unit of randomization is the team within a hospice agency, the intervention is aimed at the hospice clinicians, and patient and family caregivers are the units of analysis. We randomize at the level of the hospice to reduce cross-contamination at the clinician level.

Study Design. We will compare outcomes within and across 2 large hospice agencies using a cluster randomized trial study design. Within each hospice agency, we will recruit 30 eligible FCG-patient dyads (total n=60) of patients ≥ 65 years old, an estimated life expectancy >1 month, and polypharmacy (defined as ≥ 5 regularly scheduled daily medications). [[Eligibility Criteria](#) for details]

Hospice Sites. EOL practices vary regionally.^{13 15} Thus, we are partnering with two large, geographically distinct home hospice agencies to begin exploring the generalizability of SPECTORx nationally. Each agency has multiple offices serving different local regions within their states. Care Dimensions (Massachusetts) has 2 offices serving 4 counties in Eastern MA, and CNS Home Health & Hospice (Utah) has 10 offices throughout Utah. Combined, they had over 5,000 hospice admissions in 2016. Both have recently participated in a research studies. (see [Letters of Support](#))

Randomization and Attention Control. Within each of the 2 hospice agencies, we will randomize 1 office to intervention and 1 to control status. Target enrollment is 15 FCG-patient dyads at each office (total 30 FCG-patient dyads per hospice agency). As the attention control, we will refer staff in control offices to the NIA's website on "Medicines and Medication Management"³⁷ to review content and materials for use in FCG support.

4.3 JUSTIFICATION FOR INTERVENTION

High-quality, patient-centered care about medication management in hospice needs to address both medication appropriateness and FCG medication management support. We propose a novel approach that trains hospice staff to (a) regularly **review, simplify, and align** patients' prescribed medications with their goals of care as their illness progresses,¹⁶ and (b) **support** FCGs' with education that empowers them to understand each medication's use, develop skills for safe administration, and understand when stopping medications may be beneficial.^{3 26}

4.4 END-OF-STUDY DEFINITION

A FCG participant is considered to have completed the study if he or she has completed the baseline assessment, and at least the 2 week assessment and the post-death follow-up assessment (or at 6 months if patient survives 6 months after hospice admission).

A patient participant is considered to have completed the study if he or she has completed the baseline assessment, and at least the 2-week assessment.

The end of the study is defined as completion of the 6-month follow-up assessment shown in the Schedule of Activities (SoA), **Section 1.3**.

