8 STUDY ASSESSMENTS AND PROCEDURES

8.1 ENDPOINT AND OTHER NON-SAFETY ASSESSMENTS

The endpoint of the study is either patient death, disenrollment from hospice, or completion of 6 months of follow-up after study enrollment.

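### Section 4.4 gives caregivers no completion route at live discharge from hospice, although the synopsis and 8.1 end participation there; satisfaction with care is then unscheduled too

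*Combined protocol and SAP*

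**What the plan says.** Two places name live discharge as an end of participation. The synopsis (1.1, Participant Duration) gives a participant's time on study as "time from enrollment to patient death, discharge from hospice, or end of study". Section 8.1 says: "The endpoint of the study is either patient death, disenrollment from hospice, or completion of 6 months of follow-up after study enrollment".

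Two places leave it out. For a caregiver who has done baseline, section 4.4 sets this further condition for completion: "and at least the 2 week assessment and the post-death follow-up assessment (or at 6 months if patient survives 6 months after hospice admission"). The Schedule of Activities (1.3) heads its last column "24 weeks or death". In that schedule the row "FCG/Satisfaction with Care (Likelihood to recommend") carries one mark only, in the close-out column.

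The synopsis states "Primary Endpoint: Trial completion" and describes the primary outcome as "feasibility and acceptability of the trial as measured by trial enrollment and completion". Its secondary outcomes include "Family caregiver satisfaction with care, as determined by likelihood to recommend". Section 9.4.2 lists retention among the feasibility quantities without giving a numerator or denominator. For patients, 4.4 asks only for the baseline and 2-week assessments.

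**The concern.** Live discharge was foreseen, since it is named twice as a stopping point, but the rule that decides who completed does not provide for it. A caregiver who misses nothing can therefore be scored the same as one who refused or could not be reached. In a feasibility trial the completion rate is meant to show whether the procedures can be carried out, and a discharge from hospice says little about that. Section 9.4.2 also explores differences by site, so a difference in discharge between sites could look like a difference in retention.

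The second consequence does not depend on how the primary endpoint is defined. If follow-up ends at discharge, satisfaction with care has no scheduled measurement for any caregiver of a patient discharged alive.

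**Working it through.** **Tracing one case.** Take a patient discharged alive at week 10 whose caregiver completed baseline and weeks 2, 4, 6 and 8.

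- Under 1.1 and 8.1, participation ends at week 10. Neither a post-death nor a 6-month assessment takes place, so 4.4 scores the caregiver as a non-completer. The 1.3 close-out is triggered by neither death nor 24 weeks, so satisfaction is not collected.
- If follow-up instead continues, the caregiver can complete under 4.4 after the death or at 6 months. The synopsis and 8.1 are then wrong.

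Either way, some of the text has to change.

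**Size, if follow-up ends at discharge.** The enrollment target reproduces: 2 agencies x 2 offices x 15 dyads = 60. The documents give no survival or discharge rate, so the following are assumptions: median survival 2, 3 or 6 months; 5%, 10% or 20% discharged alive by 6 months; constant competing hazards; enrollment of 60; no assessment otherwise missed.

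- Death hazard per day: L = ln 2 / (median in months x 30.44).
- Discharge hazard G: solved so that G/(L+G) x [1 - exp(-182.6(L+G))] equals the assumed share.
- Completion ceiling with a discharge route: exp(-14(L+G)).
- Loss from the missing route: G/(L+G) x [exp(-14(L+G)) - exp(-182.6(L+G))].

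Base case, median 3 months and 10% discharged:

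- L = 0.693/(3 x 30.44) = 0.00759; G = 0.00109; L+G = 0.00868; G/(L+G) = 0.1258.
- Ceiling with a discharge route: exp(-14 x 0.00868) = 0.8855, or 88.6%.
- Loss: 0.1258 x (0.8855 - 0.2049) = 0.0856, or 8.6 points; 60 x 0.0856 = 5.1 caregivers.
- Ceiling under 4.4 as written: 0.8855 - 0.0856 = 0.7999, or 80.0%.

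A simple check: 10% discharged in total, less 1.44% discharged before day 14, leaves 8.56%. The other 11.4 points (100 - 88.6) are deaths and discharges before day 14. They are not part of this point, and the fix leaves them unchanged.

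Range of the loss:

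| Median survival | 5% discharged | 20% discharged |
|---|---|---|
| 2 months | 4.1 points (2.5 of 60) | 16.0 points (9.6 of 60) |
| 6 months | 4.5 points (2.7 of 60) | 17.7 points (10.6 of 60) |

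Satisfaction scores with no scheduled collection: 60 x 0.05 = 3 to 60 x 0.20 = 12.

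**Time origin.** The 6-month point runs from hospice admission in 4.4 and from enrollment in 8.1, and it is 24 weeks in 1.3. If enrollment falls 0 to 14 days after admission (assumed), the dates in days from admission are 182.6, 182.6 and 168 at no lag, and 182.6, 196.6 and 182 at a 14-day lag. The largest gap is 14.6 days. This is a consistency point with almost no effect on scoring.

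**The case against.** **Separating the reasons.** A reader might infer that live discharge would be irretrievably mixed with refusal and loss to follow-up. The documents do not support that. Section 7.2 requires the reason for discontinuation or withdrawal to be recorded, 7.3 codes loss to follow-up as its own primary reason, and 5.5 monitors withdrawal apart from completion. The data to separate the routes should exist, so what remains is how they are reported.

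**The primary endpoint.** A reader might also infer that the primary endpoint is certainly mis-scored. No passage ties it to 4.4. Sections 3 and 9.1 word it as completion of assessments, where the problem need not arise. The Participant Duration entry in the synopsis treats discharge as one way of finishing the study tasks, and a sponsor could score on that basis. This stands as a limit, although 4.4 is the only explicit completion rule.

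**Section 7.1.** It keeps participants who stop the intervention in later assessments. Because the hospice team delivers the intervention, discharge might be read as stopping it. But 7.1 does not mention hospice discharge, and reading it that way still contradicts the synopsis and 8.1.

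**Early deaths.** Section 4.4 also fails caregivers whose patient dies before week 2, and 5.4 expects some quick deaths. So 4.4 was never a pure measure of adherence. That is true, but no other section contradicts the plan there. On live discharge the plan contradicts itself.

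**The table and the numbers.** The 1.2 schema is not shown and the columns of 1.3 are not cleanly aligned, so the position of the satisfaction mark is the likely reading rather than a certain one. The magnitude is largely the assumed discharge share restated.

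**Conclusion.** The contradiction is in the text and holds without any outside figure. If follow-up ends at discharge, as the synopsis and 8.1 state, 4.4 makes completion impossible for an adherent caregiver of a patient discharged alive after week 2, and 1.3 schedules no satisfaction score for that caregiver.

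If caregiver completion and retention use 4.4, the rate is lowered by about 4 to 18 points under the assumed 5-20% discharge. The individual ceilings, such as 80.0% against 88.6%, depend on the model and should not be read as forecasts.

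It would go too far to say that a go or no-go decision would change: the plan sets no completion threshold, so what is affected is the meaning of the rate. Nor does the point reach patient completion, which needs only baseline and week 2. It should be fixed because the correction is small and caregiver completion has no single meaning until it is made.

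**What to change.** The sponsor should choose one reading and reconcile 1.1, 1.3, 4.4 and 8.1.

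- **If follow-up ends at discharge:** add a third route to 4.4, a close-out assessment at disenrollment from hospice, and change the 1.3 close-out heading to *24 weeks, death or disenrollment*, so that satisfaction is collected as well.
- **If follow-up continues after discharge:** keep the 4.4 routes and amend the synopsis and 8.1 to say so.

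Under either reading, use one time origin for the 6-month point. State in 9.4.2 that caregiver completion and retention use the reconciled 4.4 definition. Report live discharge separately from withdrawal and loss to follow-up, using the reasons already recorded.

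The first option costs one sentence in 4.4, one column heading, and one extra use of the existing close-out call per live discharge (3 to 12 of 60 at the assumed rates). The second costs a phrase each in the synopsis and 8.1, calls after discharge, and another source for the items taken from the hospice record. Either adds a sentence or two to 9.4.2.
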